#### 7.9 Qualitative Assessments

Not applicable.

#### 7.10 Withdrawal Criteria

Participants are free to withdraw from the trial at any time without giving explanation. Date and time of withdrawal will be recorded on the source document worksheet by the usual care team. In this instance, there will be no further collection of patient reported outcome measures or spirometry testing, but we will continue to collect healthcare utilisation data and mortality until 90 days post randomisation (unless the participant states otherwise). Participants who have withdrawn from the trial after meeting the primary outcome (fully weaned from NIV including no relapse within 48 hours of removal of NIV) will not be replaced.

#### 7.11 Storage and Analysis of Clinical Samples.

There is no requirement to store any clinical samples.

Blood gas samples will be analysed and disposed of as per local Trust guidelines.

#### 7.12 End of the Trial

The end of the recruitment phase will be when 164 patients are recruited. The follow up phase will end 90 days after the last patient is randomised.

#### 8. Trial Treatments

#### 8.1 Control Arm: Standard weaning

During weaning, arterial blood gases are performed at the end of a period off NIV to help direct the duration of subsequent breaks from NIV. ABG's can be performed at each stage of the standard (stepwise) weaning protocol, and if satisfactory, the participant can receive progressively longer intervals without NIV. Typically, at least one ABG is performed daily to determine the amount of time off NIV each day. An ABG may be omitted, if a justified clinical improvement is observed that allows progress to the next weaning step. More than one weaning step may happen in a day. Once the patient has managed a full day without support, they receive a final night on NIV. When NIV is discontinued the following morning, PtcCO2 monitoring is applied to the patient for 12 hours. Provided the patient remains stable, NIV will not be replaced.

The weaning time endpoint is the date and time that the NIV mask is removed from the patient's face for the last time (provided NIV does not need to be recommenced within 48 hours). Perform an ABG within 4 to 24 hours after the NIV mask is removed for the final time.

ISRCTN: 64639614 IRAS: 313485 CPMS: 53277

Some centres include a period of standby NIV after weaning, when the ventilator is kept at the bedside, with a subsequent ABG after 24 hours off NIV to confirm safe removal of the ventilator. This is entirely acceptable, but is not included in the weaning time.

Medical treatment will be optimised before and during NIV treatment. NIV will be delivered in spontaneous/timed pressure support mode. Supplementary oxygen will be strictly titrated to maintain  $SpO_2$  88-92% when on and off NIV (ideally controlled oxygen off NIV).

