## viii. Key Words

Non-Invasive Ventilation	Ventilation delivered via a face mask connected to a
(NIV)	ventilator to help patients to breathe out a build-up of the
	waste gas carbon dioxide.
Chronic Obstructive	A lung disease causing breathlessness, sputum production
Pulmonary Disease	and frequent flare-ups (exacerbations).
(COPD)	
Acute Hypercapnic	Respiratory acidaemia diagnosed via arterial blood gas
Respiratory Failure	(quantified by pH<7.35 and PaCO 2 (carbon dioxide) >6.0kPa.
(AHRF)	
NIV Outcomes Score	A clinical risk stratification tool to predict mortality in patients
(NIVO score)	with exacerbation of COPD complicated by AHRF and
	requiring NIV treatment.
Standard weaning versus	Patients will be randomised between these two weaning
accelerated weaning	protocols, standard weaning and accelerated weaning.
Time to successful	Duration from the baseline arterial blood gas confirming
weaning	selection criteria is met, to final removal of the ventilator.

IRAS: 313485 CPMS: 53277

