#### 3.3 Primary outcome

Time to successful weaning: duration from the baseline ABG confirming selection criteria are met, to final removal of the ventilator. Weaning will be considered successful when there has been no recurrence of AHRF requiring replacement of NIV within 48 hours of discontinuation of NIV. Recurrent AHRF more than 48 hours after removal of the ventilator will be considered relapse. Death precludes weaning and will be captured in a competing risk analysis.

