#### For the outcome of the ABG:

pH≥7.35, leave the patient off NIV, continue PtcCO2 monitoring for a further 8 hours. If there are no signs of substantial clinical deterioration, and the PtcCO2 does not rise by >1kPa, then the ventilator and PtcCO2 monitoring can be removed from the bed space.

pH<7.35, replace the NIV mask on the patient and recommence ventilation, and repeat a 4-hour weaning trial the next day. 4-hour weaning trials are completed daily until successful.

An ABG should be performed during the 4-hour trial after NIV removal or during the 8-hour monitoring after a successful ABG if: 1) PtcCO2 rises by >1kPa, or 2) there is clinical concern, but any transient reasons for deterioration (e.g. coughing, mucus plugging) should be addressed first.

The weaning time endpoint is the date and time that the ABG is taken that confirms the first successful 4 hour weaning trial (provided NIV does not need to be recommenced within 48 hours).

Medical treatment will be optimised before and during NIV treatment. NIV will be delivered in spontaneous/timed pressure support mode. Supplementary oxygen will be strictly titrated to maintain  $SpO_2$  88-92% when on and off NIV (ideally controlled oxygen off NIV).

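### The primary event time is worded differently in the two arms: it is open which episode counts after a late relapse, and the clock stops about 4 hours apart relative to mask removal

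*Protocol*

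**What the plan says.** Section 3.3 gives one definition for both arms: "duration from the baseline ABG confirming selection criteria are met, to final removal of the ventilator". The Key Words entry says the same. Section 3.3 then adds a success rule, "Weaning will be considered successful when there has been no recurrence of AHRF requiring replacement of NIV within 48 hours of discontinuation of NIV", and separates what comes later: "Recurrent AHRF more than 48 hours after removal of the ventilator will be considered relapse". Relapse is the first secondary outcome in section 3.4.

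The treatment sections restate the event by arm.

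- Standard arm (8.1): "The weaning time endpoint is the date and time that the NIV mask is removed from the patient's face for the last time", with the proviso "provided NIV does not need to be recommenced within 48 hours".
- Accelerated arm (8.2): "The weaning time endpoint is the date and time that the ABG is taken that confirms the first successful 4 hour weaning trial", with the same proviso.

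Section 8.2 also makes mask removal the start of the 4-hour trial and places the blood gas at its end. Section 7.10, on withdrawal, treats the primary outcome as met once the participant is fully weaned with no relapse in the 48 hours after NIV removal.

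**The concern.** Two things differ between the arm rules.

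The first is which episode is timed. Take a participant who is off NIV for more than 48 hours, relapses, and goes back on. In the accelerated arm the word *first*, together with the proviso, fixes the event at the first success. In the standard arm the words *last* (8.1) and *final* (3.3, Key Words) can be read as carrying the event to the end of the second course, days later. The proviso says what happens if NIV restarts within 48 hours. It does not mention a restart on, say, day 5.

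The second is which act is timed: mask removal in one arm, and a blood gas about 4 hours after mask removal in the other.

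The trial is open-label and the primary comparison is a time difference with a 24-hour target. Anyone deriving event times from the arm-specific text could handle late relapsers differently by arm, and would in any case apply the 4-hour difference to every weaned participant.

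**Working it through.** **Design figures first.** Inputs from section 10.1: weaning incidence 0.50 (standard) and 0.667 (accelerated) at 2.71 days, death 0.054 in both arms, two-sided 5%, 80% power, 10% dropout. Exponential times are assumed.

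- Total hazard = −ln(1 − F_wean − F_death)/2.71. Weaning hazard = total × F_wean/(F_wean + F_death).
- Standard: −ln(0.446)/2.71 = 0.2979; × 0.500/0.554 = 0.2689 per day.
- Accelerated: −ln(0.279)/2.71 = 0.4710; × 0.667/0.721 = 0.4358 per day.
- Cause-specific hazard ratio = 0.4358/0.2689 = 1.62.
- Events = 4(1.960 + 0.842)²/(ln 1.6205)² = 134.7, so 135. The protocol gives 69 + 67 = 136.
- Eventual weaning probabilities are 0.903 and 0.925 (mean 0.914). N = 134.7/0.914 = 147.4, so 148; 148/0.9 = 164.4, so 165. The protocol gives 164. At 74 per arm the events are 66.8 and 68.5, matching 67 and 69.

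The sample size reproduces and does not depend on this point.

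**Late relapsers under each text**

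| Text | Event for NIV restarted after 48 h |
|---|---|
| 3.3 and Key Words, *final removal* | Literally, the end of the second course |
| 3.3, success and relapse sentences | First removal that held 48 h; later NIV is relapse |
| 7.10 | Outcome already met at 48 h |
| 8.1, *last*, with proviso | Either reading |
| 8.2, *first successful*, with proviso | First success |

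**Size if the literal reading were applied.** There is no true difference; both arms follow the standard-arm hazards. Relapse among those weaned is equal in both arms, at 4.5% or 15% (the range across centres in section 2). The protocol does not give the delay to final mask removal, so it is assumed: 48 h + 31.5 h = 79.5 h (3.3 days), 48 h + 95.5 h = 143.5 h (6.0 days), or longer (8 days). The 31.5 and 95.5 h are section 2's range for duration of ventilation. Only standard-arm relapsers are moved. The sHR comes from a large simulation (400,000 per arm), with deaths kept in the risk set and no censoring. The gap is the standard median minus the accelerated median.

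| Relapse | Delay (days) | sHR, relapse rule only | Gap (h) | sHR, with 4 h offset | Gap (h) |
|---|---|---|---|---|---|
| 0 | – | 1.00 | 0 | 0.97 | −3.8 |
| 4.5% | 3.3 | 1.03 | 5.0 | 0.995 | 1.2 |
| 4.5% | 6.0 | 1.05 | 4.8 | 1.01 | 1.0 |
| 4.5% | 8.0 | 1.06 | 4.9 | 1.02 | 1.2 |
| 15% | 3.3 | 1.10 | 18.3 | 1.06 | 14.0 |
| 15% | 6.0 | 1.16 | 20.0 | 1.12 | 15.8 |
| 15% | 8.0 | 1.19 | 20.2 | 1.15 | 16.1 |

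**Check of the medians by hand.** Before any moved event has occurred, standard-arm incidence is (1 − r) × 0.9025 × (1 − exp(−0.2979t)). Setting this to 0.5 gives t = 2.91 days at r = 0.045, a gap of (2.91 − 2.71) × 24 = 4.8 h. At r = 0.15, t = 3.54 days and the gap is (3.54 − 2.71) × 24 = 19.9 h. Both agree with the simulation where the delay exceeds the median.

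**On the other reading**, where both clocks close at the first removal lasting 48 h, the late-relapse effect is zero and only the 4-hour offset remains (sHR about 0.97).

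**The case against.** The strongest reply is that the text, read as a whole, already settles the matter. Both arm rules carry the 48-hour proviso, which would be redundant if *last* meant never again. Section 3.3 classes later recurrence as relapse, a separate outcome, and section 7.10 treats the primary outcome as met at 48 hours. The two words also have ordinary meanings within each arm. In standard weaning the mask comes off repeatedly for breaks, so *last* marks the end of the stepwise wean. In accelerated weaning trials repeat daily, so *first successful* separates success from failed trials. Section 8.1 also asks for a blood gas 4 to 24 hours after final mask removal, which staff could not schedule if finality depended on a relapse days later.

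Most of this stands. It makes the first removal lasting 48 hours the more natural reading and probably the intended one. It does not remove the literal wording from the Key Words, 3.3 and 8.1, and it does not touch the 4-hour difference.

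A reader might infer more: that the plan favours accelerated weaning, or conceals relapse, its main expected harm. The documents do not support either. The late-relapse effect arises only on the less natural reading, the 4-hour offset runs the other way, and relapse is reported as the first secondary outcome.

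**Conclusion.** The inconsistency is real and should be settled before event times are derived. It is a clarification, not an established bias.

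The certain part is the time stamp: about 4 hours against accelerated weaning for every weaned participant, an sHR of about 0.97 when the strategies are equivalent. The conditional part is late relapse: zero on the natural reading, and an sHR of 1.03 to 1.19 towards accelerated weaning on the literal one. Taken together on the literal reading, the range is about 0.995 to 1.15. At the low end of relapse the two effects roughly cancel. At 15% relapse the remaining gap in medians is 14 to 16 hours, which is not small against the 24-hour target.

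These sizes rest on assumed delays to final mask removal, equal relapse in both arms and exponential times. The 4.5 to 15% range describes centres in a cohort that was not limited to low or medium NIVO risk, so it indicates scale only.

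**What to change.** Reconcile the Key Words entry, section 3.3, section 8.1 and section 8.2 to one rule for both arms: the event is the date and time of the first NIV mask removal followed by 48 hours without NIV being recommenced. NIV after 48 hours counts only as relapse and in total duration of ventilation. Drop the *last* and *final* wording from the event definition, and keep the 4-hour blood gas as confirmation of success rather than as the time stamp. The 48-hour condition by itself excludes weaning breaks and failed trials.

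The cost is a wording change in four places and one derivation rule. Mask removal times are already to be recorded (section 7.6, Table 1), so no new data are needed, and the planned 164 participants and 136 events stay as they are. Accelerated-arm times become about 4 hours shorter. Standard-arm times for late relapsers become shorter only if the literal rule would otherwise have been used. The change concerns how the endpoint is derived and does not alter patient management.

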## **Standard Weaning**

**JSUAL CARE** 

Pre-NIV: arterial or capillary blood gas required showing pH<7.35, PaCO2>6.5kPa ("NIVdecision blood gas" for NIVO score and minimisation criteria). Provide brief participant information sheet.

Confirm ready to wean: After 24+ hours of NIV, 60-minute trial of unsupported breathing with arterial or capillary blood gas at the end ("qualifying blood gas" for inclusion criteria & randomisation).

Recommence NIV at the end of 60-minute unsupported breathing trial.

Recruit: confirm all eligibility criteria met, provide full participant information and obtain consent.

## Randomisation

Depending on clinical response, continue 30 to 60 minutes breaks off NIV or progress directly to step 2

Step 2

If arterial blood gas\* satisfactory, extend breaks off NIV to 2 to 4 hours

Step 3

If arterial blood gas\* satisfactory, extend breaks off NIV to 4 to 6 hours

Step 4

If arterial blood gas\* satisfactory, remain off NIV all day, on NIV overnight

Step 5

NIV discontinued in the morning, with PtcCO2 monitoring for 12 hours. Provided the patient remains stable, NIV is not replaced.

Perform blood gas at end of standard weaning (4 to 24 hours after removal of NIV mask).

Some centres include a period of standby NIV after weaning, when the ventilator is kept at the bedside. This is entirely acceptable, but is not included in the weaning time.

More than one step may happen in a day. Target SpO2 88-92% at all times when on and off NIV.

\*During weaning, arterial blood gases are performed at the end of a period off NIV to help direct the duration of subsequent breaks from NIV. Typically, at least one ABG is performed daily. An ABG may be omitted, if a justified clinical improvement is observed that allows progress to the next weaning step.

## 8.2 Intervention Arm: Accelerated weaning

The accelerated weaning protocol involves a daily 4-hour unsupported breathing trial with transcutaneous carbon dioxide tension (PtcCO2) monitoring throughout, and an ABG taken at the end of the 4-hour period.

Following randomisation, PtcCO2 monitoring is applied to the patient and sufficient time allowed to stabilise the trend of carbon dioxide (up to 20 minutes). Physiological measurements are recorded (RR, SpO2, FiO2, PtcCO2). The NIV mask is then removed from the patient (start of the 4-hour weaning trial), and once the patient is stable off NIV with oxygen titrated to SpO2 88-92%, the physiological measurements are repeated (10 to 30 minutes off NIV). If there are no signs of substantial clinical deterioration, and the PtcCO2 does not rise by >1kPa, then the physiological measurements will be repeated at 4 hours after NIV removal, and an ABG taken (end of the 4-hour weaning trial).

#### For the outcome of the ABG:

pH≥7.35, leave the patient off NIV, continue PtcCO2 monitoring for a further 8 hours. If there are no signs of substantial clinical deterioration, and the PtcCO2 does not rise by >1kPa, then the ventilator and PtcCO2 monitoring can be removed from the bed space.

pH<7.35, replace the NIV mask on the patient and recommence ventilation, and repeat a 4-hour weaning trial the next day. 4-hour weaning trials are completed daily until successful.

An ABG should be performed during the 4-hour trial after NIV removal or during the 8-hour monitoring after a successful ABG if: 1) PtcCO2 rises by >1kPa, or 2) there is clinical concern, but any transient reasons for deterioration (e.g. coughing, mucus plugging) should be addressed first.

The weaning time endpoint is the date and time that the ABG is taken that confirms the first successful 4 hour weaning trial (provided NIV does not need to be recommenced within 48 hours).

Medical treatment will be optimised before and during NIV treatment. NIV will be delivered in spontaneous/timed pressure support mode. Supplementary oxygen will be strictly titrated to maintain  $SpO_2$  88-92% when on and off NIV (ideally controlled oxygen off NIV).

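### The primary endpoint clock stops at last mask removal in the standard arm but about 4 hours after it in the accelerated arm, so the benefit of accelerated weaning is understated by about 4 hours

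*Protocol*

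**What the plan says.** Section 3.3 gives one primary outcome for both arms: "duration from the baseline ABG confirming selection criteria are met, to final removal of the ventilator". The Key Words table has the same definition. Success also requires no recurrence of respiratory failure needing NIV within 48 hours of stopping.

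The treatment sections then set the stop time arm by arm.

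- **Standard arm (8.1):** "The weaning time endpoint is the date and time that the NIV mask is removed from the patient's face for the last time". What follows removal does not move the clock. A blood gas comes later ("Perform an ABG within 4 to 24 hours after the NIV mask is removed for the final time"), and of a standby period with the ventilator at the bedside the protocol says "This is entirely acceptable, but is not included in the weaning time".
- **Accelerated arm (8.2, outcome of the ABG):** "The weaning time endpoint is the date and time that the ABG is taken that confirms the first successful 4 hour weaning trial". The same section places mask removal at the beginning of the trial, "The NIV mask is then removed from the patient (start of the 4-hour weaning trial", and the blood gas at its end: "the physiological measurements will be repeated at 4 hours after NIV removal, and an ABG taken (end of the 4-hour weaning trial". If the pH criterion is met, the patient stays off NIV.

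Section 10.1 sizes the trial on medians of 2.71 and 1.71 days. Section 10.3.2 makes a Fine-Gray model, with death as the competing event, the primary analysis.

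**The concern.** The start of the clock, the qualifying blood gas, is common to both arms. The stop is not. In a successful accelerated trial, the mask removal that opens the trial is also the last mask removal, so the recorded time includes about 4 hours already spent off NIV. In the standard arm, time off NIV after the last removal is never counted.

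The recorded difference between arms is thus the true difference in time on NIV less about 4 hours. At stake are the size of the primary treatment effect and possibly the power to detect it. Section 4 says the trial will give a definitive result; an attenuated effect makes a false conclusion of no benefit more likely. Because section 3.3 words the endpoint in a third way, an analyst working from that section alone could also derive a different variable from one working from section 8.

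**Working it through.** **1. The offset, from the text.** Put the last mask removal at time 0 in each arm.

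| | Standard (8.1) | Accelerated (8.2) |
|---|---|---|
| Mask off for the last time | 0 h | 0 h (start of the successful trial) |
| Blood gas after removal | 4 to 24 h, not counted | about 4 h, sets the endpoint |
| Recorded clock stop | 0 h | about 4 h |

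Offset = 4 − 0 = 4 h, against accelerated weaning. Relative to the target: 4/24 = 17%. Relative to the assumed accelerated median: 4/(1.71 × 24) = 4/41.04 = about 10%. A true mask-removal difference of 24 h is recorded as 24 − 4 = 20 h. A recorded difference of 24 h needs a true one of 24 + 4 = 28 h.

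**2. Reproducing the planned sample size.** Inputs from section 10.1: at t = 2.71 days, cumulative incidence of weaning 0.50 (standard) and 0.667 (accelerated), death 0.054 in both arms; two-sided alpha 5%, power 80%, 10% attrition. With constant cause-specific hazards,

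h = [F_wean / (F_wean + F_death)] × [−ln(1 − F_wean − F_death)] / t.

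- Weaning: 0.2689 and 0.4358 per day, ratio 1.62.
- Death: 0.0290 and 0.0353 per day.
- Events (Schoenfeld): 4 × (1.960 + 0.842)² / (ln 1.6205)² = 134.7, so 135.
- Long-run probability of weaning: 0.9025 and 0.9251, mean 0.914. Patients: 135/0.914 = 148, or 74 per arm.
- With 10% attrition: 148/0.9 = 165, against 164 stated.
- Events with 74 per arm: 66.8 and 68.5, against 67 and 69 stated.

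The stated figures reproduce, so these hazards are a fair base for the next step.

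**3. Effect on power if the 24 h target is a mask-removal difference.** Simulation with those hazards, 74 per arm, and 4 h added to every accelerated-arm weaning time.

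| Test | No offset | With 4 h offset |
|---|---|---|
| Log-rank, deaths censored | about 79% | 67–69% |
| Fine-Gray score test | about 50% | 36–41% |

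The ranges cover repeated independent runs; a run of 20,000 trials gave 68% and 39%. The 50% for Fine-Gray without any offset belongs to this constant-hazard set-up and is a separate matter; only the fall is at issue here.

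**4. Sensitivity to shape.** With Weibull weaning times of shape 1.5 and the same medians (an assumption), log-rank power goes from 98% to 94%. Fine-Gray loses about 10 to 12 points, from a starting level that depends on how deaths are modelled. The direction is stable; the size is not.

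**5. If the 24 h target is already on the recorded scale.** Power at N = 164 is as planned, but the trial then rests on a true mask-removal difference of about 28 h.

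**The case against.** The best defence is that each rule times the decision to stop. In the accelerated arm the mask comes off for a trial, and staying off is decided only at the blood gas. In the standard arm the decision precedes the final removal. Both rules are explicit, so site staff are not left guessing. That rationale is arguable, but the protocol does not offer it, and it sits badly with the rest of the text. The standard arm also has 12 hours of transcutaneous monitoring and a later blood gas, none of which counts, and success in both arms is settled only in retrospect at 48 hours.

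Three further points stand. The bias is conservative. The power loss is conditional: section 10.1 derives weaning time by the protocol's definition and does not say on which scale the 24-hour gain was set. And the loss depends on the assumed distribution.

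A reader might also infer a gap of up to 12 hours from section 3.3, because the ventilator leaves the bed space in the accelerated arm only after 4 + 8 = 12 hours off NIV. The documents do not support this. It compares ventilator removal in one arm with mask removal in the other. The standard arm also has 12 hours of monitoring after removal, and standby at some centres. Applied to both arms, the literal definition gives a gap near zero, or one favouring accelerated weaning where standby is used.

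**Conclusion.** The point holds. The primary endpoint carries an arm-dependent offset of about 4 hours, 17% of the 24-hour target, which understates the benefit of accelerated weaning. This follows from sections 8.1 and 8.2 alone, taking the blood gas at its scheduled time; the actual offset moves with the actual sampling time. Nothing in the protocol explains or corrects it, and section 3.3 and the Key Words, read literally, match neither arm's rule.

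A lower power is not established outright. It holds if the target is a mask-removal difference, and the figures in the table hold for constant hazards with 74 evaluable patients per arm. On the other reading the sample size stands, at the price of a true difference of about 28 hours.

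Nor do the documents support reading this as a threat to a positive result: a finding in favour of accelerated weaning would be conservative.

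**What to change.** Use one stop time in both arms: the date and time the mask is removed for the last time, with no NIV restart within 48 hours. In the accelerated arm this is the start of the successful 4-hour trial; the blood gas confirms success but does not set the time. Put the same sentence in the Key Words, 3.3, 8.1 and 8.2. State in Table 1 (section 7.6) that the recorded date and time of NIV removal means the last mask removal, since the table does not say which removal it is. State in section 10.1 that the 24-hour target is a difference on this scale.

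The cost is a protocol amendment to the timestamp of the primary endpoint, which may have to go through the substantial-amendment route described in sections 13.1 and 13.10. No weaning step, monitoring period or blood gas changes, and the NIV-removal time is already among the recorded data.
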